**Table 1. Details the content covered in each assessment**

Information Collected	Assessments					
	Enrollment	App	Baseline	Week 8	Week 16	Week 24
Children						
Demographics	X					
Vaccine Status				X	X	X
Participant (Parent/Caregiver)						
Contact Information	X			X		
Consent	X					
Demographics		X				
Vaccine hesitancy			X		X	
Intent to vaccinate			X		X	
Perceived Benefits of Vaccination			X		X	
Perceived Risks of Vaccination			X		X	
Trusted organizations			X		X	
Disease avoidance behaviors			X		X	
Perceived app usability				X		
Adherence		X				
Household/Family						
Maternal Education			X			
Insurance			X			
Vulnerable Household Members			X			
COVID-19 Status			X		X	
COVID-19 History			X		X	
Challenges			X		X	

[figure not shown]
## 8. STUDY INTERVENTION

### 8.1 SOFTWARE, FUNCTIONALITY, AND CONTENT OF THE INTERVENTION

**Overview:** Participants in the Vaccine Uptake and General Health app arms will receive access to different mobile apps designed to provide health information. Content of the Vaccine Uptake app will focus on vaccine uptake, while content of the General Health app will focus on infection prevention and general child health.

#### 8.1.1 APP SOFTWARE

The Nebraska App Team will build the Vaccine Uptake and General Health apps using custom software created by [name] (protocol chairs) as a decision-support tool. The software creates pathways (i.e., decision trees) by linking together a series of question cards in which the user's response determines the next step. For the Vaccine Uptake App, the decision trees will be customized according to the user's demographic information entered at registration, language preference (English or Spanish), and local context (state vaccination program stage/tier by age, local vaccination sites' contact information, vaccination endorsement by local leaders and clinic staff, etc.). After the initial use session in which users complete their registration, the app will remember their registration characteristics and renders the pathways accordingly for every subsequent use. Figure 7 outlines how individual user and site data contribute to the presentation of customized app content.

---

**Figure 7.** Schema of how individual user and site data contribute to the presentation of customized content in the Vaccine Uptake app.

### 8.1.2 CONTROL (GENERAL HEALTH APP)

Specific elements of the General Health app will include:

- **Push notifications:** The app will deliver messages directly to participants' mobile devices prompting them to vaccinate their child and directing them to view specific app content (8 weeks with weekly push notifications; 2 monthly push notifications for 2 months [1 notification per month]).
- **Content areas:** Specific topics presented as pathways are outlined in the schedule of push notifications (Table 2), but the general categories of topics included are:
  - General infection prevention and mitigation measures
  - General child health topics
  - General COVID-19 information from the "How to Protect Yourself & Others" page for COVID-19 on the CDC website: <https://www.cdc.gov/coronavirus/2019-ncov/prevent-getting-sick/prevention.html>.
  - Table 2 shows the schedule of push notifications during the study period (intervention topics may change according to qualitative interview feedback)

---

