**Description of Study Intervention:**

- **Vaccine Uptake App:** 24-week (8 weeks with weekly push notifications; 2 monthly push notifications for 2 months [1 notification per month]; 8 weeks without) exposure to a mobile phone application (app) designed to improve parental knowledge, attitudes, and self-efficacy regarding pediatric COVID-19 vaccination. The app will address logistical and motivational barriers to pediatric COVID-19 vaccination. Participants will also receive eight weekly nudges (cues to action) regarding vaccinating their child that will be sent to participants via push notifications to their mobile devices. Through branching logic, users will access content tailored to their COVID-19 vaccine knowledge and confidence gaps, locality, degree of rurality-urbanicity, primary language (English/Spanish), race/ethnicity, and child's age.
- **General Health App:** 24-week (8 weeks with weekly push notifications; 2 monthly push notifications for 2 months [1 notification per month]; 8 weeks without) exposure to a mobile phone app designed to provide information on general pediatric health and infection prevention and mitigation strategies based on recommendations from the American Academy of Pediatrics (AAP) and the Centers for Disease Control and Prevention (CDC). Nudges regarding these topics will be sent to participants via push notifications to their mobile devices.

[figure not shown]
**Study Duration:** 24 months (6 months study start-up; up to 8 months rolling enrollment; 7 months final participants' completion; 3 months analysis)

**Title:** Improving pediatric COVID-19 vaccine uptake using an mHealth tool: a randomized, controlled trial

**PI:** [name]

**Participant** 28 weeks (8 weeks with weekly push notifications; 2 monthly push notifications for 2 months  
**Duration:** [1 notification per month]; 8 weeks without notifications; 4 weeks participant vaccine status follow-up)

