### **3. RISK/BENEFIT ASSESSMENT**

#### **3.1 KNOWN POTENTIAL RISKS**

This study poses minimal risk to participants (see definition of participants in Abbreviations & Definitions). Participants (in both the Vaccine Uptake app and General Health app arms) will provide protected health information (PHI) (e.g., children's names, dates of birth, and dates of vaccination) to the study team. While the study team will make every effort to store this electronic information in secure electronic databases and physical documents in secure facilities, there remains a risk of accidental as well as mandated disclosure of PHI.

Participants will view content and answer questions related to the COVID-19 pandemic that may provoke some emotional stress or anxiety relating to the pandemic and/or COVID-19 vaccination.

The study will expose participants to content providing guidance in accordance with the most current recommendations from the CDC/ACIP. This information is subject to change. While educational content for both arms will undergo revisions in real time, participants may not always choose to access updated information after the study team posts it. In addition, app content will likely recommend vaccination with the COVID-19 vaccine while it is still available under FDA EUA rather than FDA approval for some of the participants based on their age.

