#### **3.3 ASSESSMENT OF POTENTIAL RISKS AND BENEFITS**

We do not anticipate significant health risks to participants and will make every effort to minimize the possible risks described in Section 3.1. The benefit of understanding the effect of a vaccine-education mHealth tool on

**Title:** Improving pediatric COVID-19 vaccine uptake using an mHealth tool: a randomized, controlled trial

**PI:** [name]

promoting pediatric COVID-19 vaccination uptake outweighs the risks. Standards of medical care provided to participants' children will not be altered based on participants' study-related activities.

This protocol minimizes risks to participants by (a) correctly and promptly informing participants about risks (Section 3.1, above) so that they can join in partnership with the researcher in recognizing and reporting harms; (b) having staff properly trained in administering study procedures that may cause psychological distress, such as survey administration; and (c) providing safety monitoring.

If the FDA issues new warnings or precautions or withdraws EUA/approval for any of the COVID-19 vaccines for any of the included pediatric age groups during the study, the study team will take responsive action. Actions will include prompt notification of participants via at least one of the following methods: app push notification, text message, phone call, email, registered mail, as well as possibly study termination depending on the severity of the concern, as determined by the PIs and data safety monitoring board (DSMB).

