## 5. STUDY DESIGN

### 5.1 OVERALL DESIGN

This multi-site, parallel, randomized, controlled trial will assign parents/caregivers of children eligible to receive COVID-19 vaccine seen at participating clinics to receive either the mHealth Vaccine Uptake app or the General Health app containing general infection and child health topics. Randomization will be stratified by site using a permuted block design with varying block size. Outcome is receipt of COVID-19 vaccine by the parents'/caregivers' children.

[figure not shown]

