### 5.2 SCIENTIFIC RATIONALE FOR STUDY DESIGN

**Rationale for a randomized trial:** Based on the Health Belief Model and prior evidence, factors contributing to individuals' vaccine hesitancy, confidence, and/or refusal likely are multi-factorial and vary widely across individuals. Randomization of participants to the Vaccine Uptake or the General Health app study arms, outlined further below, is designed to minimize selection bias of individuals with specific attitudes or beliefs into a single study arm. For example, individuals who have lower vaccine hesitancy may be at baseline more interested/open to participating in the Vaccine Uptake study arm, whereas individuals with greater hesitancy may be more likely to decline. This potential bias ideally will be minimized by having participants consent to engaging in whatever study arm to which they are randomly assigned.

**Rationale for using the mHealth app platform developed at UNMC in the intervention and control study arms:** Most parents/caregivers, including those in rural areas, have access to a mobile device and the internet (see Section 2.1, Background). Prior studies support the feasibility of deploying app-based interventions aimed at increasing vaccination rates. Based on community feedback and our team's experience deploying app-based interventions for COVID-19 symptom screening, ensuring that the app imposes a low data burden is important

to maximizing uptake. Consequently, the platform developed at the UNMC uses data at only four time points: 1) initial download/registration (approximately 200-300 megabytes), 2) recording of sessions (2-3 kilobytes/session), 3) push notifications (2-3 kilobytes/notification), and 4) periodic updates (20-30 kilobytes/update). Thus, our mHealth app platform incurs a very low data demand, which minimizes the barrier to use for participants.

**Rationale for use of a control mHealth app:** Participants in the General Health app arm will receive access to an mHealth app to ensure similarity in access to intervention materials (e.g., sending out of a link to register for app access via the same platforms) and barriers to access (e.g., low technology literacy, lack of an internet-capable device). The goal is to compare the impact of the customized, targeted content over generic information on an app, not the ability to access content on an educational app.

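### Protocol 8.1.2 has the control app's push notifications prompt caregivers to vaccinate, contradicting the synopsis; if COVID-19 prompts reach controls, the contrast is narrower than the one the trial was sized for

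*Protocol*

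**What the plan says.** Protocol 8.1.2 lists the elements of the control app. Its first bullet says that push notifications are delivered to caregivers' "mobile devices prompting them to vaccinate their child and directing them to view specific app content", on a schedule of eight weekly and two monthly messages.

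The synopsis (Protocol 1.1, description of the study intervention) divides the messages differently. Under the Vaccine Uptake app it says: "Participants will also receive eight weekly nudges (cues to action) regarding vaccinating their child". Under the General Health app, after naming general pediatric health and infection prevention and mitigation, it says: "Nudges regarding these topics will be sent to participants via push notifications to their mobile devices".

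Three broader statements agree with the synopsis. Protocol 5.1 describes "the General Health app containing general infection and child health topics", and SAP 3.1 uses the same words. The overview in Protocol 8.1 says that "content of the General Health app will focus on infection prevention and general child health".

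Protocol 11.2 takes 30% completion without the intervention and 40% with it. It builds the 10-point difference from the app's components and names push-notification nudges as one of them, associated with a 5% increase. It does not say whether that 5% is relative or in percentage points.

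**The concern.** The section a developer would follow to build the comparator gives it a vaccination cue, while the summary of the two arms reserves that cue for the intervention. Both statements about the control's scheduled notifications cannot be right.

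This matters because the cue is one of the ingredients that the assumed effect is built from. If caregivers in both arms are prompted to vaccinate against COVID-19, that ingredient is at least partly shared. The trial then estimates the rest of the Vaccine Uptake app over a prompted control. A null result could not be read as evidence against prompts, and a reader could not tell from the documents what the comparator was.

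Two smaller gaps leave the control's messages undefined. Protocol 8.1.2 sends the reader to Table 2 for the notification schedule, but Table 2 lists Vaccine Uptake components. Protocol 7.2 lists ad hoc alerts about vaccine availability and eligibility without naming an arm, while Protocol 8.1.3 describes such alerts under the Vaccine Uptake app.

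**Working it through.** **Texts side by side.** Only 8.1.2 and the synopsis describe the control's notifications, and they conflict directly. Protocol 5.1, Protocol 8.1 and SAP 3.1 describe app content in general terms, so they are context. Three features of the text suggest misplacement:

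- The topic categories named in 8.1.2 itself do not include vaccination.
- The matching notification bullet for the Vaccine Uptake app in 8.1.3 has no vaccination-prompt clause, although that is where one would expect it.
- The synopsis assigns the vaccination nudges to the other arm.

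**The plan's own figure.** Inputs from Protocol 11.2: 30% versus 40%, two-sided 0.05, power 0.90, 2 children per caregiver, ICC 0.60.

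- Children per arm before clustering (unpooled variance): (1.960 + 1.282)² × (0.30×0.70 + 0.40×0.60) / 0.10² = 472.8
- Design effect: 1 + (2 − 1) × 0.60 = 1.6
- Caregivers per arm: 472.8 × 1.6 / 2 = 378.3, so 379 (758 in total)
- Inflation for 15% non-use: 758 / 0.85 = 891.8, so 892

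These match the protocol. The same formula also gives the other four rows of its ICC table.

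**If the control is prompted.** No document gives the effect of a control prompt. The only related figure is the 5% in Protocol 11.2. I assume that the control gains all of it, under each reading, and that the Vaccine Uptake arm stays at 40%:

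- Relative: 30% × 1.05 = 31.5%, a difference of 8.5 points
- Percentage points: 30% + 5 = 35%, a difference of 5 points

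Power = Φ(difference / SE − 1.960), with SE = √[(p₁(1−p₁) + 0.24) / n_eff]. At 379 caregivers per arm, n_eff = 379 × 2 / 1.6 = 473.75 children.

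- 30%: SE = √(0.4500/473.75) = 0.03082; 0.100/0.03082 − 1.960 = 1.285; power 0.90
- 31.5%: SE = √(0.4558/473.75) = 0.03102; 0.085/0.03102 − 1.960 = 0.780; power 0.78
- 35%: SE = √(0.4675/473.75) = 0.03141; 0.050/0.03141 − 1.960 = −0.368; power 0.36

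| Control completion | 379 per arm, ICC 0.60 | 379 per arm, ICC 0.40 to 0.80 | 446 per arm, ICC 0.60 |
|---|---|---|---|
| 30% (no gain) | 0.90 | 0.93 to 0.86 | 0.94 |
| 31.5% (5% relative) | 0.78 | 0.83 to 0.73 | 0.84 |
| 35% (5 points) | 0.36 | 0.40 to 0.32 | 0.41 |

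The last column analyses all 892 randomized caregivers (446 per arm) and gives every one of them the full 10-point effect. On that basis power stays at or above 0.90 for a control gain of up to 0.76 points. That is generous, because the extra caregivers were added to cover up to 15% who do not use the app. If those non-users complete at 30% (an assumption), the Vaccine Uptake rate is 0.85 × 40% + 0.15 × 30% = 38.5%, and power at 446 per arm is about 0.85 with no control prompt at all. The figures at 379 per arm are therefore the ones tied to the stated design.

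**The case against.** The strongest reply is that this is a drafting slip. One clause in one bullet conflicts with one statement in the synopsis, and the broader descriptions of the control could coexist with an occasional prompt. The clause does not name COVID-19, so a reminder about routine immunization could pass as general child health. Protocol 5.2 states the aim as follows: "The goal is to compare the impact of the customized, targeted content over generic information on an app". A generic prompt might fit within generic information.

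Much of this stands. Misplaced text is the likeliest explanation, and the power figures apply only to a COVID-19 cue that works. The COVID-19 reading is still the more natural one, because the synopsis uses similar wording for the COVID-19 nudges. A probable slip in the operative specification of the comparator also still has to be corrected, because the SAP gives no notification content that would settle the matter.

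A reader might infer more than the documents support:

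- **That controls were prompted.** Nothing shows which text the app was built to. The Table 2 reference is not evidence of control content: 8.1.3 makes the same reference, so it looks like a stale cross-reference. Protocol 3.1 says that "app content will likely recommend vaccination with the COVID-19 vaccine while it is still available under FDA EUA", but that sentence names no arm.
- **That building to 8.1.2 by itself puts power below 0.90.** It does not. The prompts must also raise completion among controls. A prompt with no effect leaves power as stated.
- **That the sample size is wrong or the comparison biased.** The sample size reproduces exactly, and randomization still supports a valid comparison of whatever the two arms received.

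**Conclusion.** The contradiction between Protocol 8.1.2 and the synopsis is real, is in the current text, and should be fixed. Its effect on the trial is conditional. If COVID-19 vaccination prompts reach control caregivers, the contrast is narrower than the one behind the 30% versus 40% assumption.

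The loss of power is not fixed by the documents. Crediting controls with the whole of the plan's own 5% takes power at 379 per arm from 0.90 to 0.78 (relative) or 0.36 (percentage points). This assumes an ICC of 0.60, 2 children per caregiver and a Vaccine Uptake arm that stays at 40%. An untailored prompt may do less than the 5%, and the loss would then be smaller. The Table 2 and Protocol 7.2 points are secondary: they leave the control's messages unspecified but do not contradict the synopsis.

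**What to change.** - Reconcile Protocol 8.1.2 with the synopsis by removing the vaccination-prompt clause from the control's notification bullet. If the sponsor confirms that a generic prompt was intended, keep the clause, say which vaccines it covers, and restate the contrast and the assumed effect.
- In 8.1.2, replace the Table 2 reference with the control's own list of notification topics.
- Make Protocol 7.2 consistent with 8.1.3 on which arm receives ad hoc vaccine availability and eligibility alerts. Leave untouched the commitment in Protocol 3.3 to "prompt notification of participants via at least one of the following methods: app push notification", which covers new FDA warnings or withdrawal of authorization and applies to all participants.
- Check the control app's notification content or log. If vaccination prompts were sent to controls, report this and describe the contrast as delivered.

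The cost is wording changes in two protocol sections and one check of the app's content or log. No extra participants or procedures are needed.

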### 8.1.3 INTERVENTION EXPOSURE (VACCINE UPTAKE APP)

The intervention app will consist of 3 pathways: 1) step-wise decision support with narrative vignettes, 2) self-directed learning on each selected topic area, 3) area-specific vaccine access information and corresponding push notifications. The Health Belief Model (Section 2.3) will drive topics for the vignettes and self-directed learning. Specific content will be guided by the qualitative interviews being conducted in an ongoing study and will include (among others identified): Safety; Effectiveness and personal/family susceptibility/vulnerability; Benefits (personal, family, community); Trust, decision-making/autonomy; Availability/accessibility. The list below provides specifics of the pathways and push notifications:

- **Step-wise decision support with narrative vignettes:** Using this pathway, participants will view information about COVID-19 vaccination in the form of short stories that include images of children, healthcare providers, and family members, as appropriate. The study team will tailor images and text content of the narrative vignettes to participant registration demographics. For instance, rural White adult participants with teenage children will mostly view vignettes featuring rural, White parents, teens, and healthcare providers discussing issues noted in the qualitative study to be of interest to this demographic group. Similarly, Hispanic participants of infants will mostly view vignettes featuring Hispanic parents, infants, and healthcare providers discussing issues of interest to this demographic group, etc. As everyone benefits from gaining input from diverse sources, pathways will not exclusively

feature messengers with complete demographic concordance. Participants can review other vignettes of interest to them or explore different questions within vignettes through in-app navigational buttons.

- **Step-wise self-directed learning:** Using this pathway, the app will give participants a menu of topics. Clicking on any of these will provide the participant general information on the topic and external links derived from the CDC and local health authorities, including hyperlinks that will open an internet browser window within the app. Unlike a website frequently asked question page, users will access information through branching logic based on topic area.
- **Vaccine access:** Using this pathway, the app will give participants local vaccine availability, recommendations for vaccination (e.g., at what age children can receive the vaccine locally), links to sign-up for a vaccination appointment locally, and resources for traveling to vaccination sites, etc.
- **Push notifications:** The app will deliver messages directly to participants' mobile devices through 8 weekly and 2 monthly push notifications. These messages will direct participants to view specific app content (scheduled once weekly and once monthly, see Table 2 for topic schedule) and alert participants to local or national changes to vaccine availability or vaccination recommendations (as necessary, up to once weekly).
- **Content areas:** The study team will use the Health Belief Model (Section 2.3, Figure 3) to derive general content, and the qualitative study interviews will guide specific content, including (among others identified):
  - Vaccine Safety
  - Vaccine Effectiveness
  - Personal/family susceptibility/vulnerability to COVID-19 disease morbidity and mortality
  - Benefits of vaccination (personal, family, community)
  - Trust in government, healthcare systems regarding vaccination; decision-making/autonomy in choosing vaccination for children
  - Vaccination Availability/accessibility

